7.2.5 Measurements of Exposure and Treatment Compliance

Exposure

Exposure will be summarized by the parameters Treated Eyes and Treatment Duration.

Information about the type of eyes treated are recorded on the eCRF page 'Study Eye' at the Baseline Visit. Generally, all eligible eyes should be treated. The parameter Treated Eyes will be presented in the following categories:

- Both eyes: answer to eCRF question 'Which eye(s) will be treated' is Right Eye and Left Eye.
- Left eye only: answer to eCRF question 'Which eye(s) will be treated' is only Left Eye.
- Right eye only: answer to eCRF question 'Which eye(s) will be treated' is only Right Eye.

Treatment duration will be derived based on dates of first and last study treatment administration recorded on the 'Study Drug Dosing Dates' eCRF page. It will be calculated as

- Date of Last Study Treatment Administration – Date of First Study Treatment Administration +1. If a patient has not received any study treatment in any eye, treatment duration will be set to 0.

Compliance

The assessment of patients' compliance to the IMP will be made by determining the number of study medication vials dispensed to the patient at Day 0 baseline Visit, Week 4 Visit and the number of unused study medication vials returned at Week 4 Visit and Week 8 Visit,

respectively. This information is collected on eCRF page ‘Study Drug Dosing and Accountability’.

Compliance will be evaluated according to the following formula:

$$\text{Compliance (\%)} = 100 * \frac{\text{Number of vials dispensed} - \text{Number of unused vials returned}}{\text{Number of expected days on treatment}}$$

The number of expected days on treatment will be set to 56. For each patient, the number of vials dispensed will be derived as the sum of provided numbers in the column “# Vials Dispensed” on the eCRF Page ‘Study Drug Dosing and Accountability; the number of unused vials returned will be derived as the sum of provided numbers in the column “# Vials Unused” on the eCRF Page ‘Study Drug Dosing and Accountability’.

Compliance will be presented categorical as <80%, 80-120%, >120%.

No further analyses will be planned on compliance. All other collected data including diary information on treatment compliance will be evaluated during the BDRM for relevant protocol deviations and will be listed.

7.2.6 Study Medication

Table 3: Study Treatments’ shows the Study Treatments and how they will be labelled in all TLF outputs.

Table 3: Study Treatments

Study Treatment	Study Treatment Label
rhNGF 20µg/mL	rhNGF
Vehicle	Vehicle

7.2.7 Efficacy Variables

Primary Endpoints: SANDE Score

The Symptom Assessment in Dry Eye (SANDE) questionnaire is a short questionnaire to evaluate both dry eye intensity and frequency by using a 100 mm visual analogue scale (VAS). The patient symptoms of ocular dryness and/or irritation will be quantified on the scale based on two questions that assess both severity and frequency of symptoms.

For the assessment, the patients mark on the 100 mm VAS line the point that they feel represents their perception of their current state. The VAS score is determined by measuring in millimeters from the left hand end of the line to the point that the patient marks. The SANDE scores will be then evaluated for the 2 questions severity (0-100) and frequency (0-100).

The SANDE score will be assessed at Baseline, Week 4, Week 8 and Week 12 visit and is recorded on the eCRF page ‘Symptoms Assessment in Dry Eye’. At each visit, only one assessment is performed aggregating the situation for both eyes (i.e. no separate assessment per study eye).

Primary endpoints will be defined as:

- Change from Baseline in SANDE frequency score at Week 8
- Change from Baseline in SANDE severity score at Week 8

If at least one SANDE assessment is missing at Week 8, the values of the last post-baseline assessment (including those from unscheduled visits) with non-missing values for frequency and severity will be imputed (LOCF). No imputation is performed in case of a missing baseline value (as defined in section 7.1).

Additionally, SANDE frequency and severity scores as well as respective changes from Baseline will be evaluated without any imputation for Week 4, Week 8 and Week 12, respectively.

Co-Primary Efficacy Endpoint: Corneal Staining (NEI Scale)

As grading scale of the corneal and conjunctiva damage, the NEI/Industry Workshop guidelines will be used [2]. The cornea is divided into five sectors (central, superior, inferior, nasal and temporal), each of which is scored on a scale of 0–3, with a maximal score of 15.

Briefly, on the grading scale used grade 0 reflects normal/healthy situation, whereas grade 3 reflects a severe damage in each considered sector.

Ocular Surface Staining is assessed separately for each eye at Baseline, Week 4, Week 8 and Week 12 visit and is recorded on the eCRF page 'Ocular Surface Staining (NEI score)'.

Corneal Staining will be derived as sum of scores of the five corneal sectors (central, superior, inferior nasal and temporal) ranging from 0 to 15. Corneal Staining will only be calculated, if all 5 sector scores are available. If at least one corneal staining assessment is missing at Week 8, the values of the last post-baseline assessment (including those from unscheduled visits) with non-missing values for frequency and severity will be imputed (LOCF).

Co-Primary endpoint will be defined as:

- Change from Baseline (CFB) in Corneal Staining at Week 8 for Main Eye.

In addition, the endpoint Change from Baseline in Corneal Staining at Week 8 for Secondary Eye will be considered as descriptive supportive analysis (only for patients in Subgroup 2 eyes treated).

To estimate the between patient variability, the Individual Mean Change will be derived for the subgroup of patients in the FAS with 2 eyes treated, as:

- Mean of CFB Main eye and CFB Secondary Eye, per patient at Week 8

To estimate the within patient variability, the Individual Difference in CFB for Corneal Staining between Study Eyes will be derived for the subgroup of patients in the FAS with 2 eyes treated, as:

- CFB Main eye - CFB Secondary Eye, per patient at Week 8

Additionally, Corneal Staining scores as well as respective Changes from Baseline will be evaluated for Week 4, Week 8 and Week 12, respectively. No imputation will be envisaged for these endpoints.

Secondary Endpoints: Conjunctival Staining (NEI Scale)

As grading scale of the corneal and conjunctiva damage, the NEI/Industry Workshop guidelines will be used [2].

Both nasally and temporally, the conjunctiva is divided into a superior paralimbal area, an inferior paralimbal area and a peripheral area with a grading scale of 0–3 and with a maximal score of 9 for the nasal and temporal conjunctiva, respectively.

Briefly, on the grading scale used grade 0 reflects normal/healthy situation, whereas grade 3 reflects a severe damage in each considered sector.

Ocular Surface Staining is assessed separately for each eye at Baseline, Week 4, Week 8 and Week 12 visit and is recorded on the eCRF page 'Ocular Surface Staining (NEI score)'.

Conjunctival Staining will be derived as sum of scores of the conjunctival area (nasal-superior paralimbal, nasal-inferior paralimbal, nasal-peripheral, temporal-superior paralimbal, temporal-inferior paralimbal, temporal-peripheral) ranging from 0 to 18. Conjunctival Staining will only be calculated, if all 6 area scores are available. Both scores will be derived for each eye separately.

Secondary endpoint will then be defined as:

- Change from Baseline in Conjunctival Staining at Week 8 for the Main Eye as well as for the Secondary Eye for Week 4, Week 8 and Week 12, respectively.

No imputation will be envisaged for these parameters.

Secondary Endpoint: Tear Film Break-Up Time (TFBUT)

TFBUT will be measured by determining the time to tear break-up. The TFBUT will be measured twice during the first minute after the instillation of the fluorescein. If the 2 readings differ by more than 2 seconds a third reading is taken. The TFBUT value recorded on the eCRF Page 'Tear Film Break Up Time' will be the average of the 2 or 3 measurements.

A TFBUT > 10 seconds will represent normal values, whereas values ≤ 10 seconds are likely for Dry Eyes.

TFBUT is assessed separately for each eye at Baseline, Week 4, Week 8 and Week 12 visit.

TFBUT value as well as respective Changes from Baseline will be evaluated for Week 4, Week 8 and Week 12, respectively. No imputation will be envisaged for this parameter.

Secondary Endpoint: Corneal sensitivity

Corneal sensitivity is measured continuously in cm by the Cochet-Bonnet aesthesiometer at Day 0 and Week 8 visits in each of the four quadrants of the cornea: Superior nasal, inferior nasal, superior temporal, inferior temporal. It is assessed separately for each study eye.

Corneal sensitivity values as well as respective Changes from Baseline will be evaluated for Day 0 and Week 8 visits, respectively. No imputation will be envisaged for this parameter.

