##### 3.1.3 Route and method of administration

Administration route and dose regimen for Groups 1 and 2 will be as follows:

**Group 1:** *rhNGF 20 µg/mL*: One drop (40 µL) corresponding to 0.80 µg of rhNGF will be instilled into each eligible eye six (both eyes, if applicable) times a day (every 2h), for a total daily dose of 9.6 µg (both eyes, if applicable), for 56 consecutive days. Total dose will be 537.6 µg/56 days if both eyes are treated.

**Group 2:** *Vehicle*: One drop (40 µL) will be instilled into each eligible eye (both eyes, if applicable) six times a day (every 2h).

Enrolled patients will self-administer the eye drops at home into both eyes unless only one eye meets the eligibility criteria (in both group 1 and 2).

The Investigator will check that all patients take the IMP appropriately verifying the diary and the used and/or unused medication returned.

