### **5.2 Inclusion criteria**

To be enrolled in this study, patients must fulfil all these criteria:

1. Male or female  $\geq 18$  years old
2. Patients who are characterized by the following clinical features:
  - a. History of cataract or refractive corneal surgery in the study eye(s) in the previous 6 months;
  - b. Mean Symptom Assessment in Dry Eye (SANDE) score for severity and frequency of at least 30 at baseline
3. The same eye (study eye) must fulfill all the above criteria
4. Best corrected distance visual acuity (BCDVA) score of  $\geq 0.1$  decimal units in both eyes at the time of study enrolment
5. Female patients must have negative pregnancy urine test if at childbirth potential.
6. Only patients who satisfy all requirements for informed consent may be included in the study. Written Informed Consent must be obtained before the initiation of any study-specific procedures.
7. Patients must have the ability and willingness to comply with study procedures.

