### **5.3 Exclusion criteria**

Patients meeting any of these criteria will not be enrolled in the study:

1. Any ocular disease other than Dry Eye requiring treatment with topical medications in either eye at the time of study enrolment.
2. Any active ocular infection or active inflammation in either eye unrelated to Dry Eye.
3. Presence or history of any systemic or ocular disorder, condition or disease (with particular attention to malignancies and neuro-oncological diseases) that could possibly interfere with the conduct of the required study procedures or the interpretation of the study results.
4. Use of therapeutic or Refractive Contact lenses in either eye at the time of study enrolment;
5. History of ocular surgery in the study eye(s), excluding corneal refractive or cataract procedures, within 90 days of study enrolment.
6. Females of childbearing potential (those who are not surgically sterilized or post-menopausal for at least 1 year) are excluded from participation in the study if they meet any one of the following conditions:
  - a. are currently pregnant or,
  - b. have a positive result at the urine pregnancy test (Baseline/Day 0) or,
  - c. intend to become pregnant during the study treatment period or,
  - d. are breast-feeding or,

- e. are not willing to use highly effective birth control measures, such as: hormonal contraceptives - oral, implanted, transdermal, or injected - and/or mechanical barrier methods - spermicide in conjunction with a barrier such as a condom or diaphragm or IUD - during the entire course of and 30 days after the study treatment periods.
7. Participation in another clinical study at the same time as the present and within 30 days of study enrolment;
8. History of drug, medication or alcohol abuse or addiction.

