### **10.2 Sample size and power considerations**

Sample size was calculated by assuming at single eye level a mean difference from baseline mean SANDE scores of  $-30 \pm 20$  in the rhNGF groups versus  $-20 \pm 20$  in vehicle group (80% power,  $\alpha = 0.05$ ; 2-sided test), considering that the active comparator has already proven safe and effective in dry eye patients. The sample size has been calculated based on a 2:1 randomization by the following formula:

$$n_1 = (0.5) \times n \times (1 + k)$$

$$n_2 = (0.5) \times n \times (1 + (1/k))$$

with  $n_1$  = active treatment and  $n_2$  = vehicle and  $n = 63$  and  $k = n_1 / n_2 = 2/1 = 2$ . Therefore  $n_1 = 94,5$  and  $n_2 = 47,25$ . Assuming a 5% drop out rate, a total of 100 patients in the active arm and 50 in the vehicle arm are required. This calculation is based on one study eye per patient. Whereas also two study eyes per patient may occur, that will increase power to above 80%).

However, in order to provide the mean of detecting a significant difference also on a clinical sign of the effect of the rhNGF therapy (namely Co-primary Efficacy Endpoint cornea vital staining with fluorescein (National Eye Institute [NEI] scales)), sample size calculation was also performed by assuming, at single eye level, a mean difference from baseline in Cornea NEI scale scores of  $-3.9 \pm 2.2$  in the rhNGF groups versus  $-2.9 \pm 2.2$  in vehicle group (80% power,  $\alpha = 0.05$ ; 2-sided test), considering that the active comparator has already proven safe and effective in dry eye patients. The sample size has been calculated based on a 2:1 randomization by the following formula:

$$n_1 = (0.5) \times n \times (1 + k)$$

$$n_2 = (0.5) \times n \times (1 + (1/k))$$

with  $n_1$ = active treatment and  $n_2$ = vehicle and  $n= 76$  and  $k= n_1 / n_2 = 2/1=2$ . Therefore  $n_1= 114$  and  $n_2=57$ . Assuming a 5% drop out rate, a total of 120 patients in active arm and 60 in the vehicle arm are required. This calculation is based on one study eye per patient. Whereas also two study eyes per patient may occur, that will increase power to above 80%).

Considering the two calculations performed to determine the sample size, in this study will be enrolled 180 patients (120 patients enrolled in active arm and 60 in the vehicle arm) in order to detect both changes at the same time in the variables.

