3.6 Sample Size estimation

Sample size was calculated by assuming at single eye level a mean difference from baseline mean SANDE scores of -30±20 in the rhNGF groups versus -20±20 in vehicle group (80% power, alpha =0.05; 2-sided test), considering that the active comparator has already proven safe and effective in dry eye patients. The sample size has been calculated based on a 2:1 randomization by the following formula:

$$n1 = (0.5) \times n \times (1 + k)$$

$$n2 = (0.5) \times n \times (1 + (1/k))$$

with n1= active treatment and n2= vehicle and n= 63 and k= n1 /n2 = 2/1=2. Therefore n1= 94,5 and n2=47.25. Assuming a 5% drop out rate, a total of 100 patients in the active arm and 50 in the vehicle arm are required.

However, in order to provide the mean of detecting a significant difference also on a clinical sign of the effect of the rhNGF therapy (namely Co-primary Efficacy Endpoint cornea vital staining with fluorescein (National Eye Institute [NEI] scales)), sample size calculation was also performed by assuming, at single eye level, a mean difference from baseline in Cornea NEI scale scores of -3.9 ± 2.2 in the rhNGF groups versus -2.9 ± 2.2 in vehicle group (80% power, $\alpha = 0.05$; 2-sided test), considering that the active comparator has already proven safe and effective in dry eye patients. The sample size has been calculated based on a 2:1 randomization by the following formula:

$$n1 = (0.5) \times n \times (1 + k)$$

$$n2 = (0.5) \times n \times (1 + (1/k))$$

with $n1 =$ active treatment and $n2 =$ vehicle and $n = 76$ and $k = n1 / n2 = 2/1 = 2$. Therefore $n1 = 114$ and $n2 = 57$. Assuming a 5% drop out rate, a total of 120 patients in active arm and 60 in the vehicle arm are required. This calculation is based on one study eye per patient. (Whereas also two study eyes per patient may occur, that will increase power to above 80%).

Considering the two calculations performed to determine the sample size, in this study will be enrolled 180 patients (120 patients enrolled in active arm and 60 in the vehicle arm) in order to detect both changes at the same time in the variables.

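### SANDE is scored once for both eyes, but the same-eye rule for its entry threshold, the treatment and the assumed SANDE effect are set per eye

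*SAP*

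**What the plan says.** **Measurement.** SAP 7.2.7 says of SANDE that at each visit "only one assessment is performed aggregating the situation for both eyes (i.e. no separate assessment per study eye". Protocol 6.1 lists SANDE among the ocular examinations of both eyes, and Protocol 7.1.2 does not say whether it is scored per eye or per patient.

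**Eligibility.** In Protocol 5.2, criterion 2a (recent surgery) is tied to the study eye and criterion 2b sets a mean SANDE of at least 30. Criterion 3 then adds: "The same eye (study eye) must fulfill all the above criteria". Protocol 10.1.1 defines eligibility as holding for at least one eye.

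**Treatment.** Protocol 3.1.3: "Enrolled patients will self-administer the eye drops at home into both eyes unless only one eye meets the eligibility criteria".

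**Sample size.** Protocol 10.2: "Sample size was calculated by assuming at single eye level a mean difference from baseline mean SANDE scores". SAP 3.6 repeats the single-eye basis and gives a "mean difference from baseline mean SANDE scores of -30±20 in the rhNGF groups versus -20±20 in vehicle group (80% power, alpha =0.05; 2-sided test", with "n= 63 and k= n1 /n2 = 2/1=2". After the SANDE calculation, Protocol 10.2 adds that it rests on one study eye per patient and that a second study eye would lift power above 80%. SAP 3.6 drops both remarks from the SANDE paragraph and keeps them for corneal staining. SAP 3.7, which lists departures from and clarifications of the protocol, does not mention a patient-level SANDE.

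**Analysis.** SAP 8.2 puts the number of study eyes (one or two) into the ANCOVA as a covariate. SAP 9.5.1 repeats the ANCOVA within each group only if that covariate is significant.

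**The concern.** Three parts of the design work per eye (who qualifies, which eye is treated, what effect was assumed), while the primary symptom measure works per patient.

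Take, as an illustration, a patient operated on the right eye two months ago and on the left eye seven months ago. Only the right eye meets 2a, so only that eye is treated. The overall SANDE may reach 30 because of the left eye, and the site has no eye-specific score with which to detect this. At Week 8 the patient is again scored on both eyes together, although one never received study drug.

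At stake are an entry rule that cannot be carried out for SANDE, possible dilution of the SANDE effect in one-eye patients, and a mismatch with the co-primary endpoint. Corneal staining is taken from the Main Eye, always a study eye, and Protocol 10.5 wants efficacy judged on both variables together.

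A related gap is surgery on the fellow eye during the 12 weeks. Exclusion 5 covers "History of ocular surgery in the study eye(s), excluding corneal refractive or cataract procedures, within 90 days of study enrolment". It looks back only, concerns study eyes only, and exempts the very procedures under study. I found no text on how such surgery would be handled in the analysis, yet its symptoms would enter the same score.

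**Working it through.** **1. Reproduce the plan's figure.** Inputs from SAP 3.6: difference 30 − 20 = 10, SD 20, two-sided alpha 0.05, power 80%.

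- Per arm at 1:1: 2 × [20 × (1.960 + 0.842) / 10]² = 62.8, rounded up to 63. This matches.
- 2:1 conversion: 0.5 × 63 × 3 = 94.5 and 0.5 × 63 × 1.5 = 47.25. This matches.
- 5% dropout: 94.5 / 0.95 = 99.5 and 47.25 / 0.95 = 49.7, giving 100 and 50. This matches.

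The arithmetic is right. The question is the unit to which the 10 points and the SD apply.

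**2. Can a second study eye raise SANDE power?** Not by adding a measurement. Each patient yields one score per visit whether one or two eyes are treated, so there is no within-subject duplicate of the kind Protocol section 10 describes.

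**3. Can criterion 3 be checked?**

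| Criterion | Recorded per eye? | Same-eye check possible? |
|---|---|---|
| 2a surgery | Yes | Yes |
| 2b mean SANDE of at least 30 | No | No |

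**4. Possible dilution.** Neither quantity needed is in the documents, so both are assumed: f, the share of patients with one study eye, and w, the part of the 10-point effect that remains in the overall score of a one-eye patient. Taking 10 as the undiluted patient-level effect:

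- Mean difference: δ = 10 × (1 − f + f·w)
- Evaluable patients: 120 × 0.95 = 114 and 60 × 0.95 = 57
- Standard error: 20 × √(1/114 + 1/57) = 3.244
- Power ≈ Φ(δ / 3.244 − 1.960), with SD held at 20

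| f | w = 1 | w = 0.75 | w = 0.5 |
|---|---|---|---|
| 25% | δ 10, 86.9% | δ 9.375, 82.4% | δ 8.75, 76.9% |
| 50% | δ 10, 86.9% | δ 8.75, 76.9% | δ 7.5, 63.7% |
| 75% | δ 10, 86.9% | δ 8.125, 70.7% | δ 6.25, 48.7% |

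Power of 80% needs δ of at least 3.244 × 2.802 = 9.09. At w = 0.5 that is lost once f exceeds (10 − 9.09) / 5 = 18%; at w = 0.75, once f exceeds (10 − 9.09) / 2.5 = 36%.

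**5. Does the covariate deal with it?** A main effect for number of eyes lets the mean change differ between one-eye and two-eye patients. It leaves a single treatment effect for both. Its significance says nothing about whether the treatment effect differs by number of treated eyes, so it is the wrong trigger for the separate analyses.

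**The case against.** The strongest case against has four parts.

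- **A patient-level symptom score is a legitimate target.** Protocol 2.1 chose SANDE as a validated questionnaire, and nothing in the documents supports a right/left version. This stands. A reader might infer that a per-eye SANDE ought to be primary; the documents give no basis for that.
- **The baseline for dilution is a choice.** Protocol 10.2 bases the SANDE calculation on one study eye per patient, so the 10 points can be read as the effect in a one-eye patient. On that reading one-eye patients lose nothing relative to plan. This also stands, and it is why the table is conditional. A reader might infer that the effect is halved in one-eye patients; that would need an untreated eye with equal symptoms and a patient who averages the two.
- **There is reserve and some handling.** Enrolment is 180, not the 150 that SANDE required. SAP 6.2 defines the one-eye and two-eye subgroups, and the table list includes SANDE change by subgroup. Testing is declared exploratory in SAP 3.7. These points reduce the stakes but do not settle the unit or the entry rule.
- **Fellow-eye problems are partly screened.** Exclusions 1 to 3 cover topical treatment, active inflammation or infection, and interfering ocular disorders in either eye. That helps at entry, but it does not reach later surgery on the fellow eye.

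**Conclusion.** The inconsistency is real and worth correcting. As written, the same-eye rule cannot be carried out for the SANDE threshold, and the single-eye sample-size assumption and the claimed gain from a second study eye do not fit a score collected once per patient.

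Two stronger readings should be avoided. A reader might infer that criterion 3 is unusable; it still works for surgery under 2a. A reader might also infer that the comparison is biased in favour of one arm; the same score is used in both randomised arms, so any effect is dilution toward zero and a less clear meaning, not an imbalance.

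Dilution arises only where the untreated eye is symptomatic and the patient lets it influence the mark. Its size cannot be fixed from the documents. Taking 10 points as the undiluted patient-level effect, SD 20 and 114/57 evaluable, SANDE power runs from 86.9% (no dilution) to 48.7% (75% one-eye patients keeping half the effect). With 25% one-eye patients it is 82.4% or 76.9%, at three quarters or half retained.

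**What to change.** 1. Reconcile 2b and 3 with the single score. Either add right-eye and left-eye VAS marks beside the overall SANDE and apply 2b and 3 to the study eye, or state that 2b is a patient-level criterion outside the same-eye rule.
2. Keep the overall SANDE as the primary endpoint; treat any per-eye score as supportive.
3. In Protocol 10.2 and SAP 3.6, restate the SANDE assumption at patient level and delete the protocol's claim that a second study eye raises SANDE power. List patient-level SANDE in SAP 3.7.
4. In SAP 8.2 and 9.5.1, report the SANDE treatment effect with its confidence interval in one-eye and two-eye patients whatever the covariate shows, and add a treatment-by-number-of-eyes interaction.
5. Record cataract or refractive surgery on the fellow eye during the 12 weeks and show a sensitivity analysis without those patients. Because this excludes patients on a post-randomisation event, it should stay a sensitivity analysis.

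The cost is two extra VAS items per eye at each visit if the first option in item 1 is chosen, a short amendment, and minor analysis work. If data collection is already complete, per-eye scores cannot be recovered, but items 3 and 4 remain feasible.
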